Statistical Methods	
Sample size: Approximately 16 patients from Study NS-065/NCNP-01-201 will enter this study. Because this is an open-label extension study conducted in patients who completed Study NS-065/NCNP-01-201, the sample size is not based on any statistical considerations.
 
Analysis Populations: All analyses will be based on the actual treatment each patient received. Two populations will be defined for data analysis: the Safety Population and the Full Analysis Set (FAS).
 
Safety Population All patients who receive at least one dose of NS-065/NCNP-01 Injection 250 mg in both the dose-finding (NS-065/NCNP-01-201) and extension study (NS-065/NCNP-01-202) will be included in the Safety Population. The Safety Population is the primary analysis population for safety assessments.
 
Full Analysis Set (FAS) All patients who receive at least one dose of NS-065/NCNP-01 Injection 250 mg in both the dose-finding (NS-065/NCNP-01-201) and extension study (NS-065/NCNP-01-202) will be included in the FAS. The FAS is the

primary analysis population for clinical efficacy and exploratory PD assessments.

General Statistical Considerations:

All measurements will be analyzed based upon the type of distribution and descriptive statistics presented by dose level and time point, as appropriate. Analyses utilizing pooled dose levels may also be performed. Interim analyses for safety are planned and interim analyses for efficacy may be conducted.

Efficacy Evaluation:

The primary efficacy outcome measure (TTSTAND), as well as secondary and exploratory outcome measures, will be summarized by dose level over time using descriptive statistics. Actual values and change from Pre-Infusion Visit (from Study NS-065/NCNP-01-201) and change from Week 25 (baseline of the NS-065/NCNP-01-202 study) will be presented.

Outcomes will also be compared between NS-065/NCNP-01 Injection 250 mg and matched historical untreated controls possibly using a mixed-effects linear model.

Safety and Tolerability Evaluation:

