2. STUDY OBJECTIVES

2.1. Primary Objectives

1. To evaluate the safety and tolerability of low (40 mg/kg/week) and high (80 mg/kg/week) IV doses of NS-065/NCNP-01 Injection up to 192-week Treatment Period (up to a total of 216 weeks of treatment in Study NS-065/NCNP-01-201 and 202), in boys with DMD completing Study NS-065/NCNP-01-201.
2. To investigate the effect of low and high IV doses of NS-065/NCNP-01 Injection after an additional up to 192-week Treatment Period (up to a total of 216 weeks of treatment in Study NS-065/NCNP-01-201 and 202) on muscle strength, mobility, and functional exercise capacity, as measured by Time to Stand (TTSTAND), in boys with DMD who complete Study NS-065/NCNP-01-201 vs. matched historical controls in boys with DMD.

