10.6 Efficacy Endpoints

All efficacy analyses will be performed using the FAS population. In addition, additional analyses will utilize historical control group data from the CINRG DNHS.

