10.6.1 Primary Efficacy Objective

The primary efficacy outcome measure (TTSTAND) will be summarized by dose level over time using descriptive statistics. Actual values and change from the Pre-Infusion Visit (baseline from Study NS-065/NCNP-01-201) and change from Week 25 (baseline of the NS-065/NCNP-01-202 study) will be presented.

The TTSTAND times to perform the test will also be converted to velocities. (Note that a test result that is to be converted to velocity that the patient could not perform due to disease progression will have velocity set to zero only at the first visit where this occurs. After that visit, missing observations due to disease progression will be left as missing.). If needed, a data transformation or nonparametric approach will be performed for these assessments. Within patient changes and velocities (possibly transformed) will be tested using a one-sided paired t-test within dose level and within both dose groups combined.

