10.6.2.2 Analyses comparing NS-065/NCNP-01 patients to historical controls

A matched data set from the CINRG DNHS data will be created. The purpose of the matching is to create a group data set that corresponds in characteristics to the patients in this study. The CINRG DNHS data set includes patients from age 2 years to over 30 years old, and some have been followed for close to a decade. Therefore, it is important to create a comparator group which will allow valid group comparisons. No patient to patient matched analysis is proposed. The sole purpose of the matching is to create a historical control group which is comparable in its basic characteristics to the study patient group. The final CINRG DNHS data set is expected to have between 16 and 32 patients included with time intervals of evaluations between 6 and 15 months. TTSTAND, TTRW, TTCLIMB, NSAA, 6MWT, and QMT results will be compared between the NS-065/NCNP-01 patients and the CINRG DNHS patients possibly using mixed-effects linear

models. The TTSTAND, TTRW, and TTCLIMB times to perform the test will be converted to velocities. For a test that the patient could not perform, the velocity will be set to zero.

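### Primary objective 2 compares TTSTAND with matched historical controls, but the analysis filed under it tests only change from the boy's own baseline, and its sidedness and zero-velocity rule disagree with other sections

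*Combined protocol and SAP*

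**What the plan says.** The second primary objective (synopsis and Section 2.1) is the effect of the drug "as measured by Time to Stand (TTSTAND), in boys with DMD who complete Study NS-065/NCNP-01-201 vs. matched historical controls in boys with DMD". Section 10.5 describes safety as one of two co-primary objectives, so this comparison is the other.

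Section 10.6.1, Primary Efficacy Objective, gives descriptive summaries by dose level and then: "Within patient changes and velocities (possibly transformed) will be tested using a one-sided paired t-test within dose level and within both dose groups combined". Controls are not mentioned there. The synopsis entry for the primary efficacy assessment matches it: TTSTAND at Weeks 37 to 217 against the Pre-Infusion Visit and Week 25 of the preceding study.

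The control comparison appears elsewhere:

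- Synopsis, Statistical Methods: "Outcomes will also be compared between NS-065/NCNP-01 Injection 250 mg and matched historical untreated controls possibly using a mixed-effects linear model".
- Section 10.6: "additional analyses will utilize historical control group data from the CINRG DNHS".
- Section 10.6.2.2, under Secondary Efficacy Objectives: "TTSTAND, TTRW, TTCLIMB, NSAA, 6MWT, and QMT results will be compared between the NS-065/NCNP-01 patients and the CINRG DNHS patients possibly using mixed-effects linear" models.

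For a boy who cannot perform TTSTAND because of progression, Section 10.6.1 has "velocity set to zero only at the first visit where this occurs", and then: "After that visit, missing observations due to disease progression will be left as missing". Section 10.6.2.2 names TTSTAND among the tests converted to velocity and says: "For a test that the patient could not perform, the velocity will be set to zero".

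Section 10.1 makes every statistical test two-sided at 0.05. Section 10.3 bases all analyses on the treatment actually received. Section 3.1 moves the 40 mg/kg cohort to 80 mg/kg after Amendment 10.

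**The concern.** A paired test asks whether boys differ from their own baseline. The objective asks whether they differ from similar untreated boys. In a disease where decline is expected (Section 10.8), these questions can have opposite answers: a boy can lose velocity and still do better than he would have done untreated. A report that follows the section headings would answer primary objective 2 with a test that cannot address it.

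Two further points bear on the same endpoint. The test is one-sided with no direction stated, although improvement is a fall in time and a rise in velocity, and Section 10.1 makes all tests two-sided. The handling of a boy who can no longer stand also differs between the two sections that analyse TTSTAND, so the same boy could have two velocity series.

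The study is open-label and Section 10.7 allows efficacy interim analyses. Leaving the model and these rules open therefore leaves room for choices made after data are seen.

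**Working it through.** The plan states no power, SD or effect size for TTSTAND, and the sample size is expressly not statistical (Section 10.2), so there is no plan figure to reproduce. The numbers below are illustrations.

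**Inputs from the plan:** about 16 treated boys (10.2); 16 to 32 DNHS controls, evaluated 6 to 15 months apart (10.6.2.2); alpha 0.05 (10.1); TTSTAND every 12 weeks from Week 37 to Week 217, 16 visits (synopsis).

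**Assumed:** effects in SD of change, equal SD in both groups, one value per boy, improvement as the one-sided direction, and one-sided alpha 0.05 because Section 10.6.1 states none.

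**1. Which analysis can see slower decline.** Let controls fall by 1.0 SD and treated boys by 0.5 SD.

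- Paired test: noncentrality = -0.5 × √16 = -2.0; df 15; critical t 1.753; P(reject for improvement) = 0.00019, or 0.02%.
- Two-sample comparison, two-sided, noncentrality = 0.5 / √(1/n₁ + 1/n₂):
  - 16 vs 16: 0.5 / 0.354 = 1.414; df 30; critical t 2.042; power 0.278.
  - 16 vs 32: 0.5 / 0.306 = 1.633; df 46; critical t 2.013; power 0.359.

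If the intended direction were decline, the paired test would be further still from the objective.

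**2. Precision of the control comparison.** The 95% CI half-width is t(0.975) × √(1/n₁ + 1/n₂), in SD of change:

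- 16 vs 16: 2.042 × 0.354 = 0.72.
- 16 vs 32: 2.013 × 0.306 = 0.62.

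**3. Sidedness.** With 16 boys the critical t is 1.753 one-sided and 2.131 two-sided, so the two sections give different tests.

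**4. The zero-velocity rules, read literally.** A boy first unable at Week 97 has 11 scheduled visits from then on. Section 10.6.1 gives one zero and 10 missing values; Section 10.6.2.2 gives 11 zeros.

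For the Week 217 mean change, suppose k of 16 boys lost the test at an earlier visit and the rest keep a fraction s of baseline velocity, with equal baselines:

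- Section 10.6.1: s - 1, over 16 - k boys.
- Section 10.6.2.2: s(16 - k)/16 - 1, over 16 boys.

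| k | s | 10.6.1 | 10.6.2.2 |
|---|---|---|---|
| 2 | 0.8 | -20% | -30% |
| 4 | 0.7 | -30% | -47.5% |
| 6 | 0.6 | -40% | -62.5% |

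The plan does not say how many boys would lose the test.

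The direction depends on the summary. For one illustrative boy whose velocity falls in a straight line to zero at Week 97, a line fitted to 18 points (Weeks 0, 25, and 37 to 217 by 12) has 0.39 of the slope under the unlimited rule that it has under the first-visit rule. The ratio is 0.85 if he reaches zero at Week 169. Repeated zeros worsen a fixed-time mean but flatten a fitted line.

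**The case against.** The strongest reply is that this is mainly a matter of placement. Section 10.6.2.2 plans the TTSTAND comparison by name, the synopsis does not call it secondary, and Section 10.1 commits the final report to every objective. The word additional in Section 10.6 may mean a further data source and not a lower rank. All of that stands. A reader might infer that the control comparison is missing; it is not. What remains is that the section filed under the primary objective, and the synopsis definition of the primary assessment, answer a different question, and that the model for the right question is only possible.

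Section 10.1 lets the SAP supersede the protocol and plays down p-values. The text available has no separate SAP, so whether it settles these points cannot be checked. A reader might also infer inflated type I error. The plan does not support that, since nothing is gated on this test. The mismatch affects estimates as well as p-values, however, because change from own baseline is not a difference from controls.

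The note in Section 10.6.1 is worded generally and could be the full rule that Section 10.6.2.2 shortens. That reading is possible but unstated, so clarification is needed whichever was meant.

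It is tempting to add that the paired test would credit an inert drug in boys who improve with growth. The plan gives no basis for assuming improvement; Section 10.8 expects decline.

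Nor are by-dose analyses left wholly undefined. Section 10.3 uses actual treatment, and Section 10.6.1 also tests the doses combined. The gap is narrower: where a switched boy's later change from baseline is counted.

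**Conclusion.** The concern holds as a mismatch between primary objective 2 and both Section 10.6.1 and the synopsis definition of the primary efficacy assessment. It should be fixed. The within-patient test cannot answer an objective stated against controls. Under the assumed halving of a 1.0 SD decline it would favour the drug 0.02% of the time, against 28% to 36% for the comparison already planned. Those percentages rest on assumed SD units and a simple two-group test; the mismatch itself rests only on the text.

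The conflict over sidedness is plain on the page. The zero-velocity difference is real if both sections are read literally, and its size depends on how many boys lose the test. The harm is to how the objective is answered and reported. It is not a missing analysis or a loss of alpha control.

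**What to change.** In Section 10.6.1, and to match in the synopsis entries for efficacy assessments and statistical methods:

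- Name the treated-versus-DNHS comparison of TTSTAND velocity, doses pooled, as the analysis of primary objective 2.
- Commit to a mixed-effects model adjusted for baseline TTSTAND velocity and age. The contrast is change from the Pre-Infusion baseline (a matched baseline visit for DNHS boys) at a prespecified time point within common follow-up, reported as an estimate with a 95% confidence interval.
- Keep within-patient change as descriptive, and make any test two-sided as in Section 10.1.
- Use one zero-velocity rule for both groups. For the fixed-time contrast, set zero at every visit where the boy cannot stand because of progression, with the first-visit-only rule as a sensitivity analysis.
- Given Section 10.3, state how a switched boy's post-switch data are allocated in by-dose summaries.

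Cost: no new data collection in the trial, but more than rewording. DNHS visits 6 to 15 months apart must be aligned with 12-weekly trial visits, which may reduce the number of controls or the length of follow-up. Precision stays low, with a 95% half-width of about 0.62 to 0.72 SD before adjustment, so the change answers the stated question without making the study well powered for small differences.

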10. PLANNED STATISTICAL METHODS

10.1 General Considerations

The statistical analyses described in this section will be performed as further outlined in the Statistical Analysis Plan (SAP), which will be finalized prior to database lock. The SAP will supersede the protocol if there are any differences between the two documents in the plans for data analysis and the differences will be noted in the SAP. The SAP will be included as an appendix in the clinical study report for this protocol. Statistical analyses will be performed using SAS 9.4 or higher.

Patients will be enrolled in this study after completing Study NS-065/NCNP-01-201 and will continue with the study dose (40 mg/kg/week or 80 mg/kg/week) they received in Study NS-065/NCNP-01-201. Results for this study will be summarized by study dose.

Statistical analyses will occur at the following times:

- Every 6 months. A report for the DSMB will be produced including all safety data available at the temporary data lock. A template report will be provided to the DSMB prior to the first report, and the report formats will be updated at the DSMB's requests as the data develop. The DSMB will review completeness of efficacy data, but will not review the efficacy data itself.
- At the conclusion of the study. A summary report will be generated on all baseline characteristics, safety assessments and efficacy assessments, addressing each of the primary, secondary and exploratory objectives of the study.

All statistical tests will be performed at a two-sided significance level of 0.05 with no corrections for multiple comparisons or multiple outcomes. Note however, that since this is an early phase extension study, with a focus on safety, the emphasis will not be on statistical tests (i.e., p-values).

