10.6.2 Secondary Efficacy Objectives

10.6.2.1 Analyses of NS-065/NCNP-01 patients only

TTRW, TTCLIMB, NSAA, 6MWT and QMT will be summarized by dose level over time using descriptive statistics. Actual values and change from the Pre-Infusion Visit (baseline from Study NS-065/NCNP-01-201) and change from Week 25 (baseline of the NS-065/NCNP-01-202 study) will be presented.

The TTRW and TTCLIMB times to perform the test will also be converted to velocities. For a test that the patient could not perform, the velocity will be set to zero. If needed, a data transformation or nonparametric approach will be performed for these assessments. Within patient changes and velocities (possibly transformed) will be tested using a one-sided paired t-test within dose group and within both dose groups combined.

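### Section 10.1 makes every test two-sided at 0.05, but the within-patient efficacy tests in Sections 10.6.1 and 10.6.2.1 are one-sided, with no level, direction or exception stated

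*Combined protocol and SAP*

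**What the plan says.** Section 10.1 gives one rule for the whole analysis: "All statistical tests will be performed at a two-sided significance level of 0.05 with no corrections for multiple comparisons or multiple outcomes". It adds that p-values are not the focus of an early-phase extension study, and it provides for a later SAP: "The SAP will supersede the protocol if there are any differences between the two documents".

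Section 10.6.1 then says that within-patient changes and velocities for TTSTAND "will be tested using a one-sided paired t-test within dose level and within both dose groups combined". Section 10.6.2.1 repeats this for the secondary outcomes, which "will be tested using a one-sided paired t-test within dose group and within both dose groups combined". Both sections allow a transformation or a nonparametric method if needed. Neither gives a significance level, names the alternative hypothesis or refers back to 10.1.

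The primary efficacy objective in Section 2.1 is a comparison "vs. matched historical controls in boys with DMD". Section 10.6.2.2 covers that comparison: "results will be compared between the NS-065/NCNP-01 patients and the CINRG DNHS patients possibly using mixed-effects linear" models. It does not mention sidedness, so the two-sided rule of 10.1 applies to it.

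**The concern.** A rule that covers all tests leaves no room for an unlabelled one-sided test. An analyst who follows 10.1 and one who follows 10.6.1 can report the same data differently: a favourable result between the two cut-offs is significant for one and not for the other.

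Treating the specific section as overriding the general one does not settle the matter, because the one-sided test is still incomplete. The figure 0.05 appears in 10.1 only as a two-sided level, so one-sided 0.05 and one-sided 0.025 are both open readings. The direction is not obvious either. Improvement is a shorter time but a higher velocity, and Section 10.8 says that patients with DMD are expected to decline. If the alternative is improvement, a decline cannot be declared significant.

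Timing adds to the concern. The study is open-label (Section 5.4), interim efficacy analyses may be done (Section 10.7), and the SAP need only be final before database lock (Section 10.1). Sidedness, level and direction could therefore be chosen after efficacy results have been seen.

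**Working it through.** The plan derives no sample size or power from these tests (Section 10.2), so there is no planned figure to reproduce. The check compares the two readings.

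**Inputs**
- Two-sided level of 0.05, which is 0.05 / 2 = 0.025 in each tail (Section 10.1).
- One-sided paired t-test with no level stated (Sections 10.6.1 and 10.6.2.1). Assumption for the comparison: level 0.05, alternative improvement.
- Pooled n = 16 (Section 10.2, given as approximate).
- Assumptions for illustration: 8 per dose cohort (the current text states no split), cohorts of 6 or 9, and a pooled n of 12. The smaller pooled n is plausible because, once a patient first cannot perform TTSTAND and velocity has been set to zero, "After that visit, missing observations due to disease progression will be left as missing".

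**Formula.** A paired t-test is significant when mean change / (SD / √n) exceeds the critical t on n − 1 degrees of freedom. The smallest significant mean change, in units of the SD of the within-patient change, is t / √n.

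**Pooled, n = 16, 15 df**
- One-sided 0.05: 1.753 / √16 = 0.438 SD.
- Two-sided 0.05: 2.131 / √16 = 0.533 SD.
- Ratio: 2.131 / 1.753 = 1.216.

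**Other sizes (assumed)**

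| n | t, one-sided 0.05 | t, two-sided 0.05 | Change needed, one-sided | Change needed, two-sided |
|---|---|---|---|---|
| 6 | 2.015 | 2.571 | 0.823 SD | 1.049 SD |
| 8 | 1.895 | 2.365 | 0.670 SD | 0.836 SD |
| 9 | 1.860 | 2.306 | 0.620 SD | 0.769 SD |
| 12 | 1.796 | 2.201 | 0.518 SD | 0.635 SD |
| 16 | 1.753 | 2.131 | 0.438 SD | 0.533 SD |

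A result exactly at the one-sided 0.05 cut-off has a two-sided p-value of 2 × 0.05 = 0.10.

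**Error rate at no true change.** In 400,000 simulated trials per size, the favourable rejection rates at one-sided 0.05 and two-sided 0.05 were:
- n = 8: 0.0500 and 0.0249
- n = 12: 0.0502 and 0.0252
- n = 16: 0.0499 and 0.0250

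**The other reading.** One-sided 0.025 uses the same critical t as two-sided 0.05 (2.131 at n = 16), so the favourable threshold does not move. The direction would still have to be stated, and an unfavourable result could still not be declared.

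**The case against.** The case for leaving the text alone has four parts.

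1. **The conflict may be only apparent.** A specific section can be read as an exception to a general one, and at one-sided 0.025 the favourable cut-off equals that of 10.1. It is true that the threshold effect is then zero, so the size given here depends on the 0.05 reading. But a one-sided test at 0.025 is still not a two-sided test, and the text does not say that 0.025 is meant.

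2. **The SAP can settle it.** It may, but the precedence clause deals with differences between the SAP and the protocol. This conflict is inside the protocol, and no supplied SAP text resolves it. What the final SAP says cannot be known from these documents.

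3. **Little depends on these tests.** This largely stands. No sample size rests on them, there is no multiplicity correction, many visits and outcomes are tested, and 10.1 plays down p-values. The comparison that answers the primary efficacy objective is unaffected. This limits the weight of the point, but tests that are planned still need a definition that can be carried out.

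4. **Preferring two-sided tests is a matter of taste.** In part it is: a declared one-sided 0.05 exception would also remove the contradiction. It would, however, give up the 2.5% favourable error rate that 10.1 implies.

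The per-cohort figures also need a caution. Low-dose patients may move to the higher dose under Amendment 10, and Section 10.3 bases analyses on treatment actually received, so late-visit numbers by dose level could fall outside the assumed 6 to 9. The contradiction does not depend on those figures.

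**Conclusion.** The concern holds. Section 10.1 and Sections 10.6.1 and 10.6.2.1 conflict on sidedness in the current text, and the one-sided tests lack a level and an alternative.

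If the tests are run at one-sided 0.05 for improvement, the favourable error per test at no true change doubles from 2.5% to 5%. The mean change needed falls from 0.53 to 0.44 SD for 16 pooled patients, and from 0.84 to 0.67 SD for an assumed cohort of 8. At one-sided 0.025 there is no change in the favourable threshold.

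This should be corrected, but its reach is limited to uncontrolled within-patient tests. Confidence is high about the wording. The consequence for the final analysis depends on which reading the sponsor adopts.

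**What to change.** In Sections 10.6.1 and 10.6.2.1, replace the one-sided paired t-test with a two-sided paired t-test at the 0.05 level and leave the rest of each sentence as it is. State that any nonparametric substitute has the same sidedness and level.

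If the sponsor intends one-sided tests, Section 10.1 should name them as an exception and give the direction of the alternative for times and for velocities. A one-sided level of 0.025 is recommended, because it keeps the favourable error rate at the 2.5% that 10.1 implies. A decline still could not be declared under this option.

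Either change is wording only, in two sentences or in one added to 10.1, with no new data or visits. The cost is a stricter threshold than one-sided 0.05: the mean improvement needed is 22% larger at n = 16 (0.533 / 0.438 = 1.22) and 25% larger at n = 8 (0.836 / 0.670 = 1.25). That is the threshold 10.1 already sets.
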